2.4.5.2 Analyses of adverse events

Generalities

The primary focus of adverse event reporting will be on treatment-emergent adverse events. Pretreatment and posttreatment adverse events will be described separately.

If an adverse event date/time of onset (occurrence, worsening, or becoming serious) is incomplete, an imputation algorithm will be used to classify the adverse event as pretreatment, treatment-emergent, or posttreatment. The algorithm for imputing date/time of onset will be conservative and will classify an adverse event as treatment emergent unless there is definitive information to determine it is pretreatment or posttreatment. Details on classification of adverse events with missing or partial onset dates are provided in [Section 2.5.3](#).

Adverse event incidence tables will be presented by SOC, HLGT, HLT, and PT, sorted by the internationally agreed order for SOCs and alphabetic order for HLGT, HLT and PT within a SOC, the number (n) and percentage (%) of patients experiencing an adverse event. Multiple occurrences of the same event in the same patient will be counted only once in the tables within a treatment phase. The denominator for computation of percentages is the safety population within each treatment group.

Sorting within tables ensures the same presentation for the set of all adverse events within the observation period (pretreatment, treatment-emergent, and posttreatment). For that purpose, the table of all treatment-emergent adverse events presented by primary SOC and PT (sorted by the internationally agreed SOC order and decreasing frequency of PTs within SOCs in the sotagliflozin 400 mg group) will define the presentation order for all other similar tables unless otherwise specified. In case of equal frequency regarding PTs, alphabetical order will be used.

Analysis of all treatment-emergent adverse events

The following treatment-emergent adverse event summaries will be generated for the 26-week core treatment period and the 52 week entire treatment period respectively in the safety population.

- Overview of treatment-emergent adverse events, summarizing number (%) of patients with any
 - TEAE
 - Serious TEAE
 - TEAE leading to death
 - TEAE leading to permanent treatment discontinuation
- All treatment-emergent adverse events by primary system organ class, showing number (%) of patients with at least 1 treatment-emergent adverse event, sorted by internationally agreed order of primary system organ class
- All treatment-emergent adverse event by primary SOC, HLG, HLT, and PT, showing number (%) of patients with at least 1 treatment-emergent adverse event sorted by the SOC internationally agreed order. The other levels (HLG, HLT, PT) will be presented in alphabetical order
- Number (%) of patients experiencing TEAE(s) presented by PT, sorted by decreasing incidence of PT in the sotagliflozin 400 mg group
- All treatment-emergent adverse events by primary SOC and PT, showing the number (%) of patients with at least 1 treatment-emergent adverse event, sorted by the internationally agreed SOC order and by decreasing incidence of PTs within each SOC in the sotagliflozin 400 mg group. This sorting order will be applied to all other similar tables, unless otherwise specified
- All treatment-emergent adverse events regardless of relationship and related IMP by primary SOC, HLG, HLT and PT, showing the number (%) of patients with at least 1 treatment-emergent adverse event, sorted by the internationally agreed SOC order. The other levels (HLG, HLT, PT) will be presented in alphabetical order
- All treatment-emergent adverse events by maximal severity, presented by primary SOC and PT, showing the number (%) of patients with at least 1 treatment-emergent adverse event by severity (ie, mild, moderate, or severe), sorted by the sorting order defined above
- Common TEAEs (PTs with incidence $\geq 2\%$ in any treatment group) by primary SOC, HLG, HLT, and PT, sorted by internationally agreed order of SOCs. The other levels (HLG, HLT, PT) will be presented in alphabetic order.
- Common TEAEs (PTs with an incidence $\geq 2\%$ in any treatment group) will be provided as appropriate by primary SOC, and PT and by demographic factors including gender (Male, Female), age group (<50, ≥ 50 to <65, ≥ 65 years of age), race (White, Black or African American, Asian, other), baseline SBP category (<130 mmHg, ≥ 130 mmHg), and prior antidiabetic medication (no antidiabetic therapy, insulin, non-insulin). SOC will be sorted by internationally agreed order and the PT by decreasing incidence within each SOC in the sotagliflozin 400 mg group, as described above.
- TEAEs (PTs with incidence $\geq 5\%$ in any treatment group) by primary SOC, HLG, HLT, and PT, sorted by internationally agreed order of SOCs. The other levels (HLG, HLT, PT) will be presented in alphabetic order.

- Acute renal failure (narrow search on “Acute renal failure (SMQ)” [20000003]) by PT.

Analysis of all treatment emergent serious adverse event(s)

- All treatment-emergent serious adverse events by primary SOC, HLG, HLT, and PT, showing the number (%) of patients with at least 1 serious treatment-emergent adverse event, sorted by the internationally agreed SOC order. The other levels (HLG, HLT, PT) will be presented in alphabetical order
- All treatment-emergent serious adverse events regardless of relationship and related to IMP, by primary SOC, HLG, HLT, and PT, showing the number (%) of patients with at least 1 treatment-emergent serious adverse event, sorted by the internationally agreed SOC order. The other levels (HLG, HLT, PT) will be presented in alphabetical order

Analysis of all treatment-emergent adverse event(s) leading to treatment discontinuation

- All treatment-emergent adverse events leading to treatment discontinuation, by primary SOC, HLG, HLT, and PT, showing the number (%) of patients sorted by the internationally agreed SOC order. The other levels (HLG, HLT, PT) will be presented in alphabetical order

Analysis of adverse events of special interest

- The summaries of AESI will be presented for the 52-week entire treatment period only in the safety population.
- Pregnancy and overdose will be included in overall AE summaries if any are reported. ALT increase >3 x ULN is included in laboratory PCSA summary if any.
- In addition, the number (%) of patients with an AESI will be summarized by PT and by treatment group. Corresponding listings will be provided as appropriately.

Analysis of events of special interest

- The summaries of EOSI will be presented for the 52-week entire treatment period only in the safety population.”

CV events, bone fracture and DKA

For EOSIs that are adjudicated (ie, deaths, myocardial infarction, stroke, and unstable angina requiring hospitalization, heart failure requiring hospitalization, bone fracture, and diabetic ketoacidosis), the number (%) of patients with an EOSI positively adjudicated by CEC will be summarized by treatment group. All EOSIs sent for adjudication and/or reported by the investigators in the specific AE forms will be listed along with the adjudication outcome.

Renal events

For the EOSI renal events where selected events are adjudicated, the number (%) of patients with any renal events identified in Table 3 in Section 2.1.4.2 will be summarized by treatment group.

The following renal events will be listed along with the adjudication outcome if applicable, including events,

- i. recorded in eCRF “GFR decrease”,
- ii. recorded in eCRF “Renal Event – Dialysis”,
- iii. identified as “Renal transplant” in eCRF “Other procedure”,

Renal death will be part of all deaths specified above.

Other EOSIs

For EOSIs that are not adjudicated, the number (%) of patients with at least one event will be summarized by treatment group and by PT (as identified in Table 3 in Section 2.1.4.2).

Severe hypoglycemia will be included in the summary of hypoglycemia (See Section 2.4.5.1).

AE leading to an amputation is described in the section below.

Analysis of Amputation

The number (%) of patients with amputation will be summarized by treatment group and by PT and LLT during the study (ie, regardless of on- or post-treatment). Amputation is a procedure recorded in eCRF “Other Procedures related to Amputation”. Patients who had a procedure related to amputation will be listed.

The number (%) of patients with an “AE leading to an amputation” will be summarized by treatment group and by PT (as identified in Table 3 in Section 2.1.4.2; these PTs in Table 3 were requested by the European Medicines Agency(EMA)/ Pharmacovigilance Risk Assessment Committee (PRAC) Assessment Report, 09 February 2017). The associated list will be provided as well, with patients who had an amputation procedure flagged. “AE potentially leading to an amputation” represents the condition that may potentially lead to the amputation procedure, but not in all cases an amputation has occurred.

Analysis of pretreatment and posttreatment adverse events

- All pretreatment adverse events by primary SOC and PT, showing the number (%) of patients with at least 1 pretreatment adverse event, sorted by the internationally agreed SOC order and decreasing incidence of PTs within each SOC in the sotagliflozin 400 mg group
- All posttreatment adverse events by primary SOC and PT, showing the number (%) of patients with at least 1 posttreatment adverse event, sorted by the internationally agreed SOC order and decreasing incidence of PTs within each SOC in the sotagliflozin 400 mg group

Listings

Supportive AE listings will be provided for all AEs, SAEs, death, AEs leading to treatment discontinuation and/or death, and EOSI as appropriate. Listing of all AEs, SAEs and AEs leading to treatment discontinuation and/or death, sorted by treatment, patient identification, and onset date, will include the following information: treatment, patient identification, country, age, gender, race, BMI, primary SOC, PT, reported term, onset date, study day (relative day to the start date of double-blind treatment), AE duration, duration of exposure, intensity, corrective treatment, action taken with IMP, date of treatment discontinuation (if relevant), relationship to IMP or NIMP, outcome, date of death (if any), seriousness, seriousness criteria, and AE status (“E” for a TEAE; and “P” for an on-study post-treatment AE).

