### **10.3.3 List of criteria for permanent treatment discontinuation**

The patients may withdraw from treatment with the IMP if they decide to do so, at any time and irrespective of the reason, or this may be the Investigator's decision. Patients should discuss stopping study medication with the site before doing so in order that questions can be addressed, glycemic therapy adjusted, and a follow-up assessment arranged. All efforts should be made to document the reasons for treatment discontinuation and this should be documented in the e-CRF.

The following reasons can lead to permanent discontinuation:

- At the patient's own request (ie, withdrawal of consent for treatment)
- If, in the Investigator's opinion, continuation with the administration of the study treatment would be detrimental to the patient's well-being
- Inter-current condition that requires permanent discontinuation of the study treatment as long as the abnormality persists and if the casual relationship of the concerned event and the IMP is possible (according to the Investigator's best medical judgment)
- Deterioration of renal function (defined as increase in serum creatinine >50% from baseline) that is not recovered after a temporary IMP discontinuation for 2 weeks
- Patient requires renal replacement therapy (transplant or dialysis)
- Pregnancy (in female patients)
- Specific request of the Sponsor.

Any abnormal laboratory value will be rechecked immediately to confirm the result before a decision is made to permanently discontinue IMP for the concerned patient.

For patients who prematurely discontinue the IMP, the assessments planned at EOT visit ([Section 10.1.3.2](#)) will be performed at the premature EOT Visit scheduled preferably prior to treatment discontinuation or as soon as possible after the time of discontinuation (at the latest at the next scheduled on-site visit). In the case of premature IMP discontinuation, PK samples

should not be drawn at the premature EOT visit, neither at all subsequent visits. The reason for IMP discontinuation will be clearly specified. This Premature EOT assessment may occur at a regularly scheduled visit or at an unscheduled visit.

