#### **10.3.4 Handling of patients after permanent treatment discontinuation**

Every effort should be made to maintain patients in the study. Patients should be followed up according to the study procedures as specified in this protocol up to the scheduled date of study completion, or up to recovery or stabilization of any AE to be followed up as specified in this protocol, whichever comes later.

If a patient prematurely discontinues study treatment, a premature EOT visit (see [Section 10.1.3.2](#)) should be scheduled prior to treatment discontinuation, if possible. If not possible, the Premature EOT should be scheduled as soon as possible after treatment discontinuation. In the case of early discontinuation, no sample for measuring plasma concentration should be taken at the premature EOT visit, or at any subsequent visit. For patients who discontinue treatment but remain in the study, the remaining study visits should occur as scheduled where possible. The IRT should be notified of EOT.

All cases of permanent treatment discontinuation should be recorded by the Investigator in the appropriate pages of the e-CRF.

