2.1.4 Safety endpoints

The safety analysis will be based on the reported adverse events, hypoglycemia, acute renal failure and other safety information, such as clinical laboratory data, vital signs, electrocardiogram (ECG), physical examination and marker of intestinal transit and absorption, markers of bone and calcium metabolism, etc.

Observation period

The observation period will be divided into 4 epochs:

- The **screening** epoch is defined as the time from the signed informed consent date up to the first administration of the double-blind IMP.
- The **treatment** epoch is defined as the time from the first administration of double-blind IMP to the last administration of double-blind IMP. This epoch includes the 26-week double-blind core treatment period and the 26-week double-blind extension treatment period. The 26-week core treatment period is the time from the first administration of double-blind IMP to the last administration of double-blind IMP on or before Visit 11 (Week 26) [or Day 182 if Visit 11 (Week 26) date is missing].
- The **residual treatment** epoch is defined as the time from the last administration of the IMP to the last administration of the IMP + 15 days (1 day for hypoglycemia).

The treatment-emergent adverse event (TEAE) period will include both **treatment** and **residual treatment** epochs (See the TEAE period for the 26-week core treatment period in [Section 2.5.4](#)).

- The **posttreatment** epoch is defined as the period of time starting the day after the end of the treatment-emergent adverse event period up to the last protocol-planned visit or the resolution/stabilization of all serious adverse events (SAE), adverse events of special interest (AESI) and events of special interest (EOSI), whichever is later.

The on-study observation period is defined as the time from start of double-blind treatment until the end of the study (defined as the last scheduled visit for those who completed the study and the date collected on e-CRF page “Completion of End of Study/Follow-up” for those who did not complete the study).

The post-study observation period is defined as the time from the day after the end of the study until the resolution/stabilization of all SAE, AESI and EOSI if applicable.

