2.4.5 Analyses of safety data

The summary of safety results will be presented by treatment group. The safety data will be summarized for the 26-week core treatment period and the 52-week entire treatment period separately, unless otherwise specified.

The “observation period” defined in [Section 2.1.4](#) is applicable in all safety analyses for the classification of AEs, determination of treatment-emergent PCSA values and the last on-treatment value for the laboratory, vital sign and ECG.

General common rules

All safety analyses will be performed on the safety population as defined in [Section 2.3.2](#), unless otherwise specified, using the following common rules:

- Safety data in patients who do not belong to the safety population (eg, exposed but not randomized) will be listed separately
- The baseline value (with the exception of serum creatinine and eGFR) is defined as the last available value before the first dose of double-blind IMP. For serum creatinine and eGFR, the baseline value is defined as the average of all values before the first dose of double-blind IMP.
- PCSA values are defined as abnormal values considered medically important by the Sponsor according to predefined criteria/thresholds based on literature review and defined by the Sponsor for clinical laboratory tests, vital signs, and ECG ([Appendix B](#))
- PCSA criteria will determine which patients had at least 1 PCSA during the treatment-emergent adverse event period, taking into account all evaluations performed during the treatment-emergent adverse event period, including nonscheduled or repeated evaluations.

The number of all such patients will be the numerator for the treatment-emergent PCSA percentage.

- The treatment-emergent PCSA denominator by group for a given parameter will be based on the number of patients assessed for that given parameter in the treatment-emergent adverse event period by treatment group on the safety population.
- For laboratory parameters cited in the protocol as efficacy endpoints (including HbA1c and plasma glucose etc), PCSA summaries will not be provided. These parameters will be summarized in efficacy [Section 2.4.4](#).

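### Outside amputation, ESRD, >50% eGFR decline and all-cause death, events of special interest occurring more than 15 days after the last dose have no by-arm whole-study count

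*SAP*

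**What the plan says.** SAP 2.4.5.2 sets the period for EOSI tables: "The summaries of EOSI will be presented for the 52-week entire treatment period only in the safety population". The general rule in SAP 2.4.5 is "The safety data will be summarized for the 26-week core treatment period and the 52-week entire treatment period separately, unless otherwise specified". The same section says that the observation period of SAP 2.1.4 "is applicable in all safety analyses for the classification of AEs".

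SAP 2.1.4 defines the treatment epoch from first to last administration of IMP. It adds a residual epoch, "the time from the last administration of the IMP to the last administration of the IMP + 15 days (1 day for hypoglycemia"), and the two together form the TEAE period. It also defines an on-study observation period, from the start of double-blind treatment to the end of the study.

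For amputation, SAP 2.4.5.2 chooses a different period. Patients are counted by treatment group and "by PT and LLT during the study (ie, regardless of on- or post-treatment").

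Protocol 10.3.3 lists among the reasons for a permanent stop a creatinine rise of more than 50% "that is not recovered after a temporary IMP discontinuation for 2 weeks". Protocol 10.3.4 then says "Every effort should be made to maintain patients in the study", and Protocol 10.4.2 continues event observation to the end of the study after IMP is stopped.

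**The concern.** IMP can be stopped because of a safety outcome, renal deterioration, and the patient is then followed off drug. If the EOSI tables close 15 days after the last dose, the later adjudicated and grouped events of exactly these patients are collected but not counted by arm. Truncation that depends on a safety outcome is potentially informative. If one arm has more creatinine-driven stops, it also loses more of its later events from the comparison. What is at stake is the completeness of the descriptive by-arm comparison for cardiovascular events, fracture, DKA, VTE, malignancy and some renal events.

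**Working it through.** The plan gives no figure on this point to reproduce. The check has three parts.

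**1. Which period applies.** The EOSI sentence does not itself mention 15 days, so the window has to be inferred. SAP 2.1.4 defines the treatment epoch by dosing and says that it includes the core and extension treatment periods. SAP 2.5.4 defines the 26-week core treatment period by dosing and, separately, a 26-week core study period, so treatment and study are distinct terms in this SAP. The amputation paragraph had to say explicitly that post-treatment events count. Last dose plus 15 days is therefore the most natural reading.

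**2. What is counted by arm after that window.**

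- Amputation: whole study (SAP 2.4.5.2).
- ESRD (dialysis, sustained eGFR below 15, transplant): from Week 4 to any later time in the study, with a KM plot to end of study, ITT (SAP 2.4.4.3, Appendix D).
- eGFR decline above 50%: by visit including Week 52, with a KM plot to end of study, ITT (same places).
- Deaths: on-study, on-treatment and post-study, without adjudicated cause (SAP 2.4.5.3).
- Post-treatment AEs: n (%) by SOC and PT (SAP 2.4.5.2). These are not adjudicated and are split across terms.
- Adjudicated MI, stroke, unstable angina, heart failure, fracture and DKA; grouped VTE and malignancies; the Table 3 renal composite and sustained ≥50% eGFR decline; CV or renal death by cause: no whole-study count.

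The post-treatment AE table cannot be added to the EOSI table to give patients with an event, because one patient may appear in both.

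**3. Timing and size.** The last dose precedes the 14-day hold, so a 15-day window closes about 15 − 14 = 1 day after the creatinine recheck.

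The MDRD formula in SAP 2.5.1 has creatinine to the power −1.154. A 50% creatinine rise is an eGFR fall of 1 − 1.5^(−1.154) = 37%. A 50% eGFR fall needs creatinine multiplied by 2^(1/1.154) = 1.82. A patient stopped on the rise from baseline that applies up to Week 8 may therefore not yet meet the ≥50% renal EOSI, and may meet it later off drug. Table 3 asks for 30 days of sustained eGFR decline or 90 days of dialysis unless positively adjudicated. Both are longer than 15 days, and the table does not say which date places the event.

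Days outside the window up to Day 364 = 364 − (7 × week of last dose + 15):

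| Last dose at | Window ends | Days outside | Share of 364 |
|---|---|---|---|
| Week 4 | Day 43 | 321 | 88% |
| Week 8 | Day 71 | 293 | 80% |
| Week 12 | Day 99 | 265 | 73% |
| Week 26 | Day 197 | 167 | 46% |
| Week 39 | Day 288 | 76 | 21% |

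For an arm of 92 followed to Week 56, assume that a proportion p stops for any reason, at Week 26 on average, and stays in the study. Each such patient has 56 − 26 − 15/7 = 27.9 weeks outside the window.

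- Patient-years excluded per arm = 92 × p × 27.9 / 52.18: 4.9, 9.8 and 14.7 for p = 0.10, 0.20 and 0.30.
- Share of follow-up = p × 27.9 / 56: about 5%, 10% and 15%.

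The stop rates and the Week 26 average are assumptions; the documents give neither. The roughly two weeks that completers spend outside the window before Week 56 are left out.

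**The case against.** The word only in the EOSI sentence may chiefly mean that no 26-week EOSI table is made. The same phrase is used elsewhere in the SAP where the 26-week version is dropped, and Protocol 11.4.3.4 states no on-treatment limit. This stands as a reason to call the 15-day reading inferred. It does not extend the window, because the treatment periods in SAP 2.1.4 still end with dosing.

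A reader might infer that all special-interest outcomes are cut off. The documents do not support that: amputation is counted over the whole study in the same section. A reader might also infer that renal failure after a stop is lost, for example chronic dialysis starting weeks after the last dose. That is not so, because it is counted by arm as ESRD in ITT to end of study. The >50% eGFR decline is a close analogue of the Table 3 criterion, though not its sustained ≥50% form.

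Nor do the events disappear. They are listed with adjudication outcomes, post-treatment AEs are tabulated by PT, and the DMC reviews unblinded safety data. What is missing is a grouped, adjudicated count by arm.

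A focus on treatment-emergent events is prespecified, and Protocol 9.2 justifies the 15 days as about five half-lives in severe renal dysfunction. That is a fair reason to keep the on-treatment table. Safety is descriptive, and Protocol 4.4 does not expect clinical outcomes often enough for statistically significant information. That limits the consequence, but a descriptive comparison still benefits from complete counts.

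**Conclusion.** The point holds in a limited form. On the most natural reading of SAP 2.1.4 and 2.4.5.2, the events in the last item of the coverage list have no by-arm whole-study count, although they are collected to end of study. Amputation, ESRD, >50% eGFR decline and all-cause death are not affected.

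The 5% to 15% of follow-up is illustrative and covers stops for any reason, so it does not show that the loss falls mainly on patients with renal deterioration. It is not converted into events. A reader might infer that harm from sotagliflozin will be understated. The documents do not show this: the calculation uses equal stop rates, and any bias between arms depends on unequal stopping.

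**What to change.** In SAP 2.4.5.2, state the EOSI window explicitly, including whether it ends 15 days after the last dose and which date places a Table 3 renal event. Beside the on-treatment table, add a by-arm n (%) summary over the on-study observation period already defined in SAP 2.1.4, as is done for amputation. It should cover:

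- adjudicated MI, stroke, unstable angina, heart failure, fracture and DKA;
- VTE and special-interest malignancies;
- the Table 3 renal composite and sustained ≥50% eGFR decline;
- CV and renal death by adjudicated cause.

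The on-treatment table stays, and nothing requires the on-study table to become the main presentation. The cost is SAP wording and a few extra descriptive tables from data already collected, with no effect on alpha. The downside is that off-drug events enter the added count, which is why the two tables should be shown together.

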#### **10.4.1.4 Events of special Interest**

An EOSI is a serious or nonserious AE of scientific and medical concern specific to the Sponsor’s product or program, for which ongoing monitoring may be appropriate. Such events may require further investigation in order to characterize and understand them. These events should be reported on the specific e-CRF page (where applicable) and will only qualify for expedited reporting when serious (fulfilling SAE criteria).

The EOSIs for this study are:

- MACE (CV death, MI, or stroke) and other specific CV events (eg, heart failure leading to hospitalization)
- Severe hypoglycemia (see [Section 10.6.1](#))
- Genital mycotic infections (to include vulvovaginal candidiasis in females and candidal balanitis in males)
- Urinary tract infections
- Clinically relevant volume depletion and events related/possibly related to volume depletion
- Diarrhea
- Pancreatitis
- Bone fractures
- Venous thrombotic events, to include deep venous thrombosis and thromboembolism (to include pulmonary embolism)
- Diabetic ketoacidosis
- Renal events, to include 50% decline in eGFR, end stage kidney disease, renal death
- Malignancies of special interest (breast, bladder, renal cell, Leydig cell, pancreatic, prostate, and thyroid cancer)
- Adverse events leading to amputation.

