#### **11.4.3.4 Analyses of events of special interest**

The number (%) of patients with each EOSI event will be summarized by treatment group. All events reported by the Investigators on the AE forms for special interests will be listed along with the adjudication outcome (if applicable).

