Chronic dialysis	(3) For dialysis, (3a) dialysis lasted for ≥ 90 days (e.g. end date – start date + 1 ≥ 90) as recorded in eCRF "Renal Event – Dialysis", OR (3b) positively adjudicated by CEC: Yes to the question ". Does the subject meet the criteria for ESRD".
Renal transplant	(4) "Renal transplant" captured in eCRF "Other procedure form", where adjudication is not required. PTs of Renal transplant (10038533), Renal and pancreas transplant (10052278), Renal and liver transplant (10052279) based on MedDRA v22.0.
Renal death	(5) Renal death as positively adjudicated by CEC: "Death - Non-Cardiovascular (Renal)" as the primary cause of death

EOSI not adjudicated*

Severe hypoglycemia	algorithm specified in Section 2.1.4.1 based on eCRF "Hypoglycemic Events"
Genital mycotic infections	PTs in Appendix C
Urinary tract infections	PTs in Appendix C,

AE Grouping	Criteria
Clinically relevant volume depletion and events related/possibly related to volume depletion	PTs in Appendix C
Diarrhea	Narrow search on “Noninfectious diarrhoea (SMQ)” [20000218] plus the following PTs (MedDRA v22.0): Gastroenteritis (10017888), Antidiarrhoeal supportive care (10055660), Enteritis (10014866), Enteritis leukopenic (10014877), Enterocolitis (10014893), Enterocolitis haemorrhagic (10014896)
Pancreatitis	PTs in Appendix C
Venous thrombotic events	PTs in Appendix C
Malignancies of special interest	Breast cancer: Narrow search on “Breast neoplasms, malignant and unspecified (SMQ)” [20000149] Prostate cancer: Narrow search on “Prostate neoplasms, malignant and unspecified (SMQ)” [20000152] Leydig-cell cancer: PTs of Leydig cell tumour of the testis (10024407) and Ovarian Sertoli-Leydig cell tumour (10073270) based on MedDRA v22.0 Thyroid cancer: PTs in Appendix C Renal cell cancer: PTs in Appendix C Pancreatic cancer: PTs in Appendix C Bladder cancer: PTs in Appendix C

EOSI AE leading to an amputation

Adverse event leading to an amputation	“AE Correction” as the reason for amputation in eCRF “Other Procedures related to Amputation”
AE potentially leading to an amputation *	PTs in Appendix C

* Search terms will be updated using the MedDRA version currently in effect at Sanofi at the time of database lock for EOSI identified by them. AE potentially leading to amputation: not one of EOSI defined in protocol, included and analyzed due to their relevance in regards to lower limb complications and amputations as a requirement from health authorities.

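### SAP 2.4.5.2 gives the amputation EOSI's name to a table built from a different category's preferred terms, and plans no table for the EOSI as Table 3 defines it (minor)

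*SAP*

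**What the plan says.** **Protocol.** Section 10.4.1.4 includes "Adverse events leading to amputation" in its list of EOSIs. Section 11.4.3.4 makes the reporting commitment: "The number (%) of patients with each EOSI event will be summarized by treatment group".

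**SAP Table 3 (section 2.1.4.2).** Two rows concern amputation.
- The EOSI row is identified from the case report form: "AE Correction” as the reason for amputation in eCRF “Other Procedures related to Amputation". It has no PT list.
- The second row, "AE potentially leading to an amputation", is identified by the PTs in Appendix C. The footnote gives its status: "AE potentially leading to amputation: not one of EOSI defined in protocol, included and analyzed due to their relevance".

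**SAP 2.4.5.2.** The paragraph on other EOSIs passes this one on: "AE leading to an amputation is described in the section below". The amputation paragraphs that follow plan two things:
- a table and a listing of amputation procedures, for any reason and over the whole study;
- a table in which "patients with an “AE leading to an amputation” will be summarized by treatment group and by PT (as identified in Table 3", with a remark that these PTs came from an EMA/PRAC assessment report, and a listing in which patients who had an amputation procedure are flagged.

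The last sentence describes the potential category and says that an amputation did not necessarily occur.

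**The concern.** The second table takes its title from one Table 3 row and its contents from the other. Two consequences follow if the programming team works from the text.

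First, a patient whose only relevant event is on the Appendix C list is counted under the EOSI's name, with or without an amputation. Second, the EOSI that the protocol names has a definition in the SAP but no output.

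The documents treat amputation as a safety question of its own. Protocol 6.3.4 sets up an independent committee to review the cases, and the Table 3 footnote cites a health-authority requirement. A table carrying this title will be read as a count of events that caused amputations, so it should contain those events and no others.

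**Working it through.** No sample size, rate or error level enters, and the plan gives no figure to reproduce. The check sets the passages side by side.

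**1. Which row does the title belong to?** The title in 2.4.5.2 matches the first Table 3 row, the EOSI. That row's only criterion is the AE-correction reason on the amputation procedure page.

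**2. Which row do the PTs belong to?** The table is by PT as identified in Table 3. The EOSI row has no PTs. The only amputation row with PTs is the potential one, through Appendix C. The EMA/PRAC attribution agrees with this, because the footnote to that row gives a health-authority requirement as the reason for including it.

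**3. What is on the list?** Counting the Appendix C entries headed as potentially leading to amputation gives 97 PTs.
- Two of them name an amputation (Amputation, Spontaneous amputation). The other 97 − 2 = 95 do not. They include Dehydration, Hypovolaemia, Paraesthesia, Diabetic neuropathy, Wound and Localised infection.
- Dehydration (10012174) and Hypovolaemia (10021137) are also on the Appendix C volume-depletion list, so one event can enter both tables.
- The list does not cover every possible cause. As printed, it has four specific cellulitis terms but no plain Cellulitis. An event that did cause an amputation could therefore fall outside the table bearing the EOSI's name, so the mismatch can undercount as well as overcount.

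**4. Is the EOSI tabulated anywhere else?**
- Other EOSIs (2.4.5.2): no, it refers the reader to the amputation paragraphs.
- Amputation procedures (2.4.5.2): this counts procedures for any reason, by procedure term, on or after treatment. The EOSI is the causing event, and 2.4.5.2 restricts EOSI summaries to the 52-week treatment period. Criterion, unit and period all differ.
- Appendix D: there is no amputation row.

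The AE-correction criterion therefore appears in the Table 3 definition and in no explicitly planned table, which does not meet Protocol 11.4.3.4.

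**The case against.** The strongest reply is that one word was left out. The regulatory attribution, the flag for patients who had an amputation (pointless if every listed patient had one) and the closing sentence on the potential category all suggest that the PT table was meant for that category. Table 3 also places both rows under one group heading that carries the EOSI's name, which may explain the slip. This is probably right, and it settles the title. It does not settle the second defect: with the title corrected, the EOSI still has no table.

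A second reply is that nothing is lost, because every EOSI patient has a record on the amputation procedure page and so appears in the procedure table and listing. EOSI listings are also planned as appropriate, Table 3 still governs how EOSIs are identified, and a blinded committee reviews the cases. This stands as far as amputations are concerned. It does not supply a count by treatment group of amputations attributed to an adverse event, or the events that caused them.

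A reader might go further and infer that the plan hides the true number of amputation-related events. The procedure table, its listing and the flag in the PT listing contradict that.

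A reader might also infer that the mislabelled table would show an excess on sotagliflozin, because two of its terms overlap with volume depletion, which Protocol Appendix B associates with SGLT2 inhibitors. The documents give no rates by arm for any listed term. Protocol 4.1 reports a smaller rise in urinary glucose excretion in CKD 3B than in the total population of that study, so the size of any such effect in CKD 4 is unknown.

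**Conclusion.** The inconsistency is real and has two parts: a table whose title and contents come from different categories, and an EOSI with a definition but no explicitly planned table. In structural terms, 97 PTs, 95 of which do not name an amputation, stand in for one eCRF criterion. The number of patients misclassified cannot be computed, because the documents give no incidence for the listed terms.

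The severity is minor. The safety summaries are descriptive, no efficacy endpoint, population or error rate is affected, and amputations themselves remain visible. It is still more than a clerical slip, because correcting the title does not produce the missing table. The conclusion rests on reading SAP 2.4.5.2 as it stands and on Appendix D adding nothing to it. An output specification outside these documents could already resolve the point.

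**What to change.** In SAP 2.4.5.2, under the analysis of amputation:

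1. Retitle the Appendix C PT table as AE potentially leading to an amputation, and state that it is not a protocol EOSI.
2. Add a table of the number (%) of patients by treatment group with the EOSI, AE leading to an amputation, using the AE-correction criterion in Table 3. Show it by PT of the causing event where the eCRF links the procedure to an event.
3. Keep the procedure table, its listing and the amputation flag in the PT listing.

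The cost is a few lines of SAP text and one small table from data already collected. No change to the protocol or the eCRF is needed.
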